### 6.6. Dose Modification

### 6.6.1. Supplemental Dosing

If a BTH event occurs during the Screening Period, the participant will be ineligible for the study. If a participant experiences BTH during maintenance treatment with ravulizumab, an additional weight-based maintenance dose of ravulizumab may be administered or the next scheduled maintenance dose may be accelerated as per Table 5 at the Investigator's discretion after discussion with the Medical Monitor.

 Table 5:
 Dosing Guidance for Patients with Breakthrough Hemolysis

			Timing of Subsequ Maintenance Dose	ent Dose after Next
Time of BTH	Supplemental Dosing	Next Maintenance Dose	if free C5 is < 0.5μg/mL	if free C5 is ≥ 0.5 μg/mL
$\leq$ 2 weeks after previous dose	Decision to be made based on results of Free C5 at Investigator's discretion	As per SoAª	As per SoA a	6 weeks after the last maintenance dose b
>2 to < 6 weeks after previous dose	Supplemental dose	As per SoA a	As per SoA a	6 weeks after the last maintenance dose b
$\geq$ 6 weeks after previous dose	Not applicable	Accelerate next dose at Investigator's discretion	As per SoAª	6 weeks after the last maintenance dose b

aTiming of next dose will be per SoA (Section 1.3)

b See Section 6.6.2

Abbreviations: BTH = breakthrough hemolysis; C5 = complement component 5; SoA = Schedule of Activities

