### 8.2.4. Clinical Safety Laboratory Assessments

• Detailed instructions on the procedure for collection, processing, storage, and shipment of the samples for laboratory analyses will be provided in the Laboratory Study Manual. All sample analyses will be performed by Alexion or its designee.

- See Section 10.2 for the clinical laboratory tests to be performed and the SoA (Section 1.3) for their timing and frequency.
- If a suspected event of BTH occurs, LDH, PK, and PD samples will be collected and analyzed. If the suspected event of BTH does not occur at a scheduled visit, an unscheduled visit should be conducted for evaluation of the participant and collection of the required LDH, PK, and PD samples.
- The Investigator must review the laboratory report, document this review, and record any clinically relevant changes occurring during the study in the AE section of the eCRF. The laboratory reports must be filed with the source documents. Clinically significant abnormal laboratory findings are those which are not associated with the underlying disease, unless judged by the Investigator to be more severe than expected for the participant's condition.
- All laboratory tests with values considered clinically significantly abnormal during participation in the study should be discussed by the Investigator and Medical Monitor.
  - If such values do not return to normal/baseline within a period of time judged reasonable by the Investigator, the etiology should be identified, and Alexion notified.
  - All protocol-required laboratory assessments, as defined in Section 10.2, must be conducted in accordance with the laboratory manual and the SoA.
  - If laboratory values from non-protocol specified laboratory assessments performed at the institution's local laboratory require a change in participant management or are considered clinically significant by the Investigator (eg, SAE or AE or dose modification), then the results must be recorded in the CRF.

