## 8.5.2. Sample Collection during Confirmation Visit Through Follow-up

Blood samples for determination of serum drug concentrations and PD assessments will be collected before and after administration of study drug at the time points as specified in the SoA (Section 1.3). The predose (within 0.5 hours prior to the start of infusion) PK/PD sample may be drawn through the venous access created for the dose infusion, prior to administration of the dose. End-of-infusion (within 0.5 hours after the end of infusion) PK/PD samples will be drawn from the participant's opposite, non-infused arm. All collection times will be recorded in the eCRF. In the event of BTH, a serum PK/PD sample will be collected.

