### 10.7. Appendix 7: COVID-19 Vaccine Risk Assessment

Following a review of the available COVID-19 vaccine data (eg, Pfizer/BioNTech, Moderna, AstraZeneca, Johnson & Johnson), it is unlikely that the immune response to a COVID-19 vaccine (and therefore, the efficacy of the vaccination) would be diminished with concomitant ALXN1210 administration, based on ALXN1210's mechanism of action. There is currently no information available evaluating the safety and efficacy of COVID-19 vaccines in participants treated with ALXN1210. The same precautions should be taken as described in Section 6.5.1. Vaccination may further activate complement. As a result, patients with complement-mediated diseases may experience increased signs and symptoms of their underlying disease. Therefore, patients should be closely monitored for disease symptoms after recommended vaccination.

Because vaccines may activate complement, if possible, consider vaccination when the underlying complement-mediated disease is clinically controlled and when systemic C5 inhibitor concentration (and subsequent complement blockade) is relatively high, shortly after administration. Local and national guidelines should be consulted for recommendations related to COVID-19 vaccination. The potential risks identified and mitigation measures put in place in light of the COVID-19 vaccination rollout are provided in Table 8.

Risks Category	Summary of Data/ Rationale for Risk	Mitigation Strategy
Potential Risks		
Data quality and integrity	Missing data due to appointments for COVID-19 vaccination or side effects of COVID-19 vaccine may impact study visit schedules, and increase missed visits and/or participant study discontinuations, inadvertently resulting in missing data (eg, for protocol-specified procedures).	Capture specific information in the eCRF that explains the reason the data is missing (eg, missed study visits due to appointments for COVID-19 vaccination or side effects of COVID-19 vaccine).

Table Ø.	Detential Dialsa	nd Mitigation	Maagunag d	luna ta i	COVID 10	Vaaina
Table o:	r otentiai risks a	nu whugation.	vieasures u	iue to v		vaccine

Abbreviations: COVID-19 = coronavirus disease 2019; eCRF: electronic case report form

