4.1. Primary Efficacy Endpoint

Proportion of participants who experience free C5-associated BTH through Day 351. Free
C5-associated BTH is defined as BTH concurrent with free C5 concentrations ≥ 0.5 μg/mL. BTH
is defined as at least 1 new or worsening symptom or sign of intravascular hemolysis (fatigue,
hemoglobinuria, abdominal pain, shortness of breath [dyspnea], anemia [hemoglobin < 10 g/dL],
major adverse vascular event (MAVE), including thrombosis, dysphagia, or erectile dysfunction)
in the presence of elevated LDH ≥ 2 × upper limit of normal (ULN).

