6.3. Missing Data

6.3.1. Missing Efficacy Endpoints

The absence of data related to BTH can only be interpreted to mean that no BTH has occurred. Thus all efficacy data will be analyzed as-is and no imputations will be performed.

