8.1. Primary Efficacy Endpoint and Analysis

The primary efficacy endpoint is the proportion of participants who experience free C5-associated BTH through Day 351.

BTH is defined as at least 1 new or worsening symptom or sign of intravascular hemolysis (fatigue, hemoglobinuria, abdominal pain, shortness of breath [dyspnea], anemia [hemoglobin < 10 g/dL], MAVE, including thrombosis, dysphagia, or erectile dysfunction) in the presence of elevated LDH, which is defined as LDH \geq 2 × ULN. The determination about whether a BTH has occurred will be reflected on the BTH form of the eCRF. In the event of a BTH outside the visit schedule, an unscheduled visit will occur, at which point all information pertaining to the BTH will be collected.

Free C5-associated BTH is defined as BTH concurrent with free C5 concentrations $\geq 0.5 \,\mu\text{g/mL}$. The first C5 concentration captured on or after the date of the BTH will be considered when defining a BTH event as free C5-associated.

The proportion of participants who experience free C5-associated BTH through Day 351 will be calculated along with a 2-sided exact 95% CI using the Clopper-Pearson method. All data will be listed.

Participants who withdraw from the study due to lack of efficacy during the Evaluation Period will be considered as non-responders and will be counted in the group with free C5 associated BTH if free C5 is ≥ 0.5 µg/mL at ET visit. For participants who withdraw from the study for any other reason during the Evaluation Period, their data up to the time of withdrawal will be used to assess free C5 associated BTH.

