The precision for the descriptive statistics of PK parameters will follow the same as the aforementioned descriptive statistics of ravulizumab concentration (see Section 9.2.4).

This document is confidential

SAP Version: 2.0 09-Feb-2023

Controlled Document ID: 3903A.02, Effective Date 31-Aug-2020

10. Pharmacodynamics

Serum samples will be collected for free and total C5 analyses (before eculizumab dosing) during Screening on Day -57 and Day -29. During the evaluation period serum free and total C5 concentrations will be collected before and after administration of study drug at the timepoints specified in the schedule of assessments (see Section 1.3 of the Protocol). In the event of BTH, a serum sample for PD analysis will be collected. In the event of an unscheduled visit, a PD blood sample will be collected as soon as possible.

Pharmacodynamic analyses will be conducted PD set.

The PD effects of ravulizumab administered IV will be evaluated by assessing the absolute values, and changes and percentage changes from baseline in total and free C5 serum concentrations over time, as appropriate. In addition, mean free C5 concentrations, and number and percentage of participants with free C5 concentrations $\geq 0.5 \, \mu \text{g/mL}$ will be presented over time.

Mean (95% CI) for absolute values, change and percentage change from baseline over time will be presented graphically for free and total C5. For free C5 boxplots will also be presented over time.

A by-participant listing will also be produced.

SAP Version: 2.0 09-Feb-2023

Controlled Document ID: 3903A.02, Effective Date 31-Aug-2020

11. Safety

The population used for safety analyses will be the Safety Set. Safety will be assessed on the basis of AE reports, clinical laboratory data, electrocardiogram (ECG) parameters, physical examinations, vital signs, and immunogenicity data, using descriptive statistics.

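### The free C5 value that classifies a BTH for the primary endpoint has no maximum interval, no condition on intervening doses and no outcome when a usable sample is lacking

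*SAP*

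**What the plan says.** SAP 4.1 and 8.1 define the primary event as "BTH concurrent with free C5 concentrations" at or above 0.5 µg/mL. BTH itself needs a new or worsening symptom or sign together with LDH of at least 2 × ULN. SAP 8.1 then states how the C5 value is chosen: "The first C5 concentration captured on or after the date of the BTH will be considered when defining a BTH event as free C5-associated". Neither section says how close in time counts as concurrent, and the rule does not refer to dosing.

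The collection instructions are stronger than the classification rule:

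- Protocol 8.2.4 and Table 2: "If a suspected event of BTH occurs, LDH, PK, and PD samples will be collected and analyzed". An off-schedule event calls for an unscheduled visit.
- SAP 10: "In the event of an unscheduled visit, a PD blood sample will be collected as soon as possible".
- Protocol 8.5.2 schedules PK/PD samples before dosing and also after it: "End-of-infusion (within 0.5 hours after the end of infusion) PK/PD samples will be drawn" from the other arm.

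On dosing after an event, Protocol 6.6.1 says that "an additional weight-based maintenance dose of ravulizumab may be administered or the next scheduled maintenance dose may be accelerated" at the Investigator's discretion, following Table 5. On missing data, SAP 6.3.1 says: "The absence of data related to BTH can only be interpreted to mean that no BTH has occurred". Efficacy data are analysed as they stand, without imputation.

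**The concern.** A date rule matches the endpoint definition only if the first C5 value on or after the event date reflects complement blockade at the event. Nothing in SAP 8.1 ensures this. Four things are left open:

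- how long after the event a C5 value may still count;
- whether a value drawn after a ravulizumab dose given since the event may count;
- what happens to a BTH with no C5 value (under SAP 6.3.1 it would simply not be counted as free C5-associated);
- which date is the BTH date (symptom onset, LDH draw or eCRF entry), and whether the value is free or total C5, since both are measured.

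The likely direction matters. Protocol 10.7 describes the state in which "systemic C5 inhibitor concentration (and subsequent complement blockade) is relatively high, shortly after administration". A sample taken soon after a dose would therefore tend to show low free C5 and turn a primary event into a non-event, which is the favourable direction. The study is open-label with sponsor staff unblinded (Protocol 6.3), so choosing after the fact which value was concurrent would be a decision made with knowledge of the results.

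**Working it through.** **1. The plan's own intervals.** Inputs: n = 20 and two-sided 95% Clopper-Pearson limits (SAP 3.3 and 8.1). Lower limit = Beta quantile (0.025; x, n − x + 1); upper limit = Beta quantile (0.975; x + 1, n − x). For x = 19, 15, 10, 5, 2, 1 and 0 this gives 75.1-99.9, 50.9-91.3, 27.2-72.8, 8.7-49.1, 1.2-31.7, 0.1-24.9 and 0-16.8%. All seven agree with the SAP table after rounding.

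**2. Scheduled C5 samples and doses (Protocol Table 2, q8w).** PK/PD is marked on Days 1, 15, 71, 127, 183 and 351. Doses are on Days 1, 15, 71, 127, 183, 239 and 295. Days 239 and 295 therefore have LDH and a dose but no routine PK/PD. Gaps between scheduled C5 days are 14, 56, 56, 56 and 168 days. On q6w dosing (Table 3), PK/PD is marked at every visit.

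**3. What the rule selects.**

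| Situation | C5 value selected | Effect |
|---|---|---|
| Event sample prompt and pre-dose | That sample | As intended |
| BTH on a dosing day with PK/PD, pre-dose tube lost | Same-day end-of-infusion value | Tends to read low |
| Day 239 or 295: BTH recognised only when the LDH result returns after the infusion | Event sample, drawn post-dose | Tends to read low |
| Day 239 or 295: event sample also missed | Day 351 value | Either direction |
| No C5 value at all | None | Not counted as free C5-associated |

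The third row needs no protocol deviation. LDH is drawn before the dose, and one qualifying sign, hemoglobin below 10 g/dL, is itself a laboratory result, so BTH may first be suspected after the infusion.

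**4. Length of the late fallback.**

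- From Day 239: 351 − 239 = 112 days; with ±7-day windows, 344 − 246 = 98 to 358 − 232 = 126.
- From Day 295: 351 − 295 = 56 days; 344 − 302 = 42 to 358 − 288 = 70.
- These do not bound the problem, because BTH can fall between visits. For Day 184, 351 − 184 = 167 days, with doses on Days 239 and 295 in between.

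**5. Effect of one reclassified participant.**

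| Analysis | Not counted | Counted | Shift |
|---|---|---|---|
| Final, n = 20 | 0/20 = 0% (0-16.8%) | 1/20 = 5% (0.1-24.9%) | 1/20 = 5 points |
| Interim, n = 10 (SAP 13) | 0/10 = 0% (0-30.8%) | 1/10 = 10% (0.3-44.5%) | 1/10 = 10 points |

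The event counts are illustrative; the documents give no expected number.

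**The case against.** The strongest reply is that the failure is conditional. PD sampling is mandated at every suspected BTH and at unscheduled visits, so the rule usually picks the right tube. Appendix 2 calls for local results when central ones are too late for dosing or response evaluation. Free C5 also guides management: in every row of Table 5 the timing of the dose after the next one depends on it, in the row for events within 2 weeks of a dose the supplemental-dose decision does too, and Protocol 6.6.2 allows q6w only after a free C5-related BTH. A missing value is therefore less likely. All BTH is a separate secondary endpoint, collection times are recorded and C5 is listed by participant, so an error could be traced.

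All of that stands and lowers the weight of the point. It does not close the gap. These are instructions for collection and management; none requires the event sample to precede a dose in general, and none is a classification rule. The visit windows in SAP 6.4 only assign records to visits. Traceability does not correct the primary proportion.

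Three stronger readings are tempting but not supported:

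- A reader might note that 6 of the 7 post-baseline q8w visits include a dose and infer that most visits are at risk. That count shows only where a post-dose or later value could be selected; it says nothing about how often.
- A reader might infer that the long Day 351 fallback affects the interim. It cannot: every scheduled visit through Day 183 has PK/PD, so at the interim only a missed or post-dose event sample matters.
- A reader might take Table 5 to mean that a BTH-prompted dose commonly precedes the sample. At the regular q8w visits an event is normally at least 6 weeks after the last dose, where Table 5 marks supplemental dosing as not applicable, so this concerns mainly unscheduled events.

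**Conclusion.** The point holds as a specification gap in the primary endpoint, of minor to should-fix weight. SAP 8.1 promises concurrency but classifies by a date rule that can accept a post-dose or much later C5 value, and it leaves events without a usable sample uncounted. It gives the intended answer whenever the event sample is prompt and pre-dose.

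The size is one participant at a time: 5 percentage points at n = 20, 10 points at n = 10. The frequency is unknown, so the documents do not support a claim that the primary result will be biased, only that it could be. The likely direction, under-counting, applies to values soon after a dose and rests on the protocol's general statement about blockade at that time.

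The Day 239 and 295 examples assume that Table 2 is right and no routine PK/PD is drawn then. SAP 9.3.1 analyses trough concentrations on both days. That conflict is a separate point to reconcile; if C5 is in fact sampled pre-dose on those days, these two examples largely fall away, while the lost-tube and unscheduled-event cases remain.

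**What to change.** Amend SAP 8.1, analysis only:

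1. Define the BTH date. Classify each event by the free C5 (not total C5) sample drawn with the qualifying LDH or, failing that, the nearest sample within a limit fixed before database lock. In either case require that no ravulizumab was given between BTH onset, or the qualifying LDH draw if earlier, and the C5 sample. Counting from onset matters: otherwise LDH and C5 tubes drawn together after a dose would still qualify. The documents supply no interval for this purpose; the 24-hour tolerance in Table 2 concerns LDH relative to a dose.
2. List BTH events without such a sample as free C5 not evaluable.
3. Add a sensitivity analysis that counts those events as free C5-associated. Apply all three steps at the interim and final analyses.

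The cost is a few sentences and one extra run on data already planned, with no new visits or samples and no change to dosing. The downside is that a few events may become not evaluable and the worst-case proportion may be slightly less favourable.

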#### 2.3.1. Risk Assessment

Risks of Clinical Significance	Summary of Data/ Rationale for Risk	Mitigation Strategy
Potential Risks		
Serious hemolysis after drug discontinuation	This potential disease-associated risk is based on a theoretical possibility, associated with abrupt ravulizumab discontinuation, resulting in a so- called rebound effect. Rebound effect is described for many biologicals but has not been observed in ravulizumab clinical trials.	The effects are most likely not completely preventable, but their severity can be minimized by avoiding abrupt drug discontinuation. Participants who discontinue the drug will be followed up for 16 weeks if participants remain in the study.
Serious infection	This potential risk is a based on the mode of action of ravulizumab and experience with the use of eculizumab. Since the relevance of serious infection with ravulizumab therapy has not been confirmed in clinical trials, this remains a potential risk.	Increased awareness of healthcare professionals and participant about the potential risk of serious Infection. Monitoring for signs and symptoms of serious infections will be conducted as part of routine safety assessments for this study.
Malignancies and hematologic abnormalities	The natural evolution of PNH disease makes PNH patients more prone to development of hematologic abnormalities or malignancies as approximately 30-70% of PNH patients eventually develop aplastic anemia or myelodysplastic syndrome. The potential role of ravulizumab in the risk of such abnormalities or malignancies (if any) is unknown	Monitoring as part of routine safety assessments for this study.
Immunogenicity	Treatment with any therapeutic protein has the potential to induce an immune response. Potential clinical consequences may include severe hypersensitivity type reactions, decrease in efficacy and induction of autoimmunity, including antibodies to the endogenous form of the protein (Casadevall, 2002; Li, 2001). Protein therapies administered IV have the potential risk of causing local (infusion-site reactions) and systemic reactions (infusion-associated reactions).	In the ALXN1210-PNH-103 and ALXN1210-PNH-201 studies, no participants have returned a positive ADA sample. ADA will be assessed. Monitoring for infusion reactions will be conducted as part of routine safety assessments for this study.

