## 7. DISCONTINUATION OF STUDY DRUG AND PARTICIPANT DISCONTINUATION/WITHDRAWAL

### 7.1. Discontinuation of Study Drug

In rare instances, it may be necessary for a participant to permanently discontinue (definitive discontinuation) the study drug. If the study drug is definitively discontinued, the participant should remain in the study to be evaluated for safety follow up. See the SoA (Section 1.3) for data to be collected at the time of discontinuation of the study drug and follow-up and for any further evaluations that need to be completed.

Participants should be considered for discontinuation from study drug if any of the following occur during the study:

- 1. Serious hypersensitivity reaction
- 2. Use of disallowed medication as defined in Section 6.5
- 3. Alexion or the Investigator deems it is necessary for the participant
- 4. Withdrawal of consent.

Participants who become pregnant must have study drug discontinued.

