### 7.2. Participant Discontinuation/Withdrawal from the Study

All efforts should be made to ensure participants are willing to comply with study participation prior to conducting the screening procedures. The study staff should notify their site monitor and Alexion of all study withdrawals as soon as possible. The reason for participant discontinuation must be recorded in the source documents and eCRF.

If a participant withdraws consent, the assessments specified for the Early Termination (ET) visit (as shown in the SoA, Section 1.3) will be performed and Alexion and site monitor notified as soon as possible. Participants who withdraw from the study will not be replaced.

Participants should be permanently discontinued from ravulizumab treatment if any of the following occur during the study:

- Serious infusion reaction (such as bronchospasm with wheezing or requiring ventilator support or symptomatic hypotension) or serum sickness-like reactions manifesting 1 to 14 days after drug administration;
- Severe uncontrolled infection;
- Pregnancy or planned pregnancy; or
- If the Alexion Medical Monitor or the Investigator deems it is in the best interest of the participant.

The Investigator should speak with the Medical Monitor prior to discontinuing a participant's study treatment. If a participant is discontinued from study drug, the participant should be encouraged to return for the remainder of his or her scheduled protocol visits until starting a different complement-targeted therapy.

If a participant is discontinued from the study with an ongoing AE or an unresolved laboratory result that, in the opinion of the Investigator, is significantly outside of the reference range and
clinically significant (Section 10.3), the Investigator will attempt to provide follow-up until a satisfactory clinical resolution of the laboratory result or adverse event is achieved.

If a female participant is permanently discontinued from ravulizumab treatment due to pregnancy, the Investigator will attempt to follow-up until the outcome of the pregnancy (Section 10.4).

- A participant may withdraw from the study at any time at his/her own request or may be withdrawn at any time at the discretion of the Investigator for safety, behavioral, compliance, or administrative reasons. This is expected to be uncommon.

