3.3. Determination of Sample Size

The proposed sample size for this estimation study is approximately 20 participants. The range of possible proportions of participants experiencing free C5-associated BTH during the Treatment Period (with 95% exact confidence intervals [CI]) is as follows:

Proportion of BTH (participants with BTH/total population)	95% CI
95% (19/20)	75%, 100%
75% (15/20)	51%, 91%
50% (10/20)	27%, 73%
25% (5/20)	9%, 49%
10% (2/20)	1%, 32%
5% (1/20)	0%, 25%
0% (0/20)	0%, 17%

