7.1. Participant Disposition and Withdrawals

The number and percentage of participants screened, failed screening, treated, completing treatment, discontinued treatment, reasons for discontinuation of treatment, completing the study, switching to q6w dosing, discontinued from the study, reasons for discontinuation, and those included in each analysis set will be summarized. The number of participants with discontinuation status impacted by COVID-19 will be included in the summary.

Screen failures are defined as participants who consent to participate in the clinical study but are not subsequently entered in the study. Individuals who do not meet the criteria for participation in this study because of a reason that is expected to resolve or has resolved may be rescreened based on discussion and agreement between the Investigator and the Medical Monitor. Rescreened participants will be assigned a new participant identification (ID) number. The ID number of the previous screen failure will be linked to the new participant ID number in the eCRF.

Completion/discontinuation status, inclusion/exclusion criteria definitions, and inclusion/exclusion criteria violations will be listed by participant.

A listing of participants showing their affiliation to the different analysis sets will also be generated.

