8.2.3. Proportion of participants with transfusion

Proportion of participants receiving a transfusion from baseline to Day 351 will be summarized along with a 2-sided 95% exact CI using the Clopper-Pearson method. Number of transfusion episodes, number of units transfused will also be summarized for participants receiving transfusions.

Participants who withdraw from the study due to lack of efficacy during the Evaluation Period will be considered as non-responders and will be counted in the group receiving transfusion. For participants who withdraw from the study for any other reason during the Evaluation Period, their data up to the time of withdrawal will be used to assess the proportion of participants receiving a transfusion.

All data will be listed.

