8.2.4. Proportion of participants with stabilized hemoglobin

Proportion of participants with stabilized hemoglobin in the absence of transfusion from baseline to Day 351 will be summarized along with a 2-sided 95% exact CI using the Clopper-Pearson method. Stabilized hemoglobin is defined as avoidance of a \geq 2 g/dL decrease in hemoglobin level from baseline in the absence of transfusion from baseline to Day 351.

Participants who withdraw from the study because of lack of efficacy during the Evaluation Period will be considered as non-responders and will be counted in the group who did not meet the stabilized hemoglobin definition. For participants who withdraw from the study for any other reason during the Evaluation Period, their data up to the time of withdrawal will be used to assess stabilized hemoglobin.

All data will be listed.

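### The lack-of-efficacy failure rules are triggered by leaving the study, not by stopping ravulizumab, so the same treatment failure can be scored differently, mainly for transfusion and stabilized hemoglobin

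*SAP*

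**What the plan says.** **Failure rules in the SAP.** Section 8.1 (primary endpoint): "Participants who withdraw from the study due to lack of efficacy during the Evaluation Period will be considered as non-responders". They join the free C5-associated BTH group only if free C5 is at or above 0.5 µg/mL at the ET visit. Section 8.2.3 (transfusion) says that such participants "will be considered as non-responders and will be counted in the group receiving transfusion", with no further condition. Section 8.2.4 (stabilized hemoglobin) opens in the same way, "Participants who withdraw from the study because of lack of efficacy during the Evaluation Period will be considered as non-responders", and again has no further condition. In all three sections, a participant who withdraws from the study for any other reason contributes data up to withdrawal. Section 8.2.1 (all BTH) and section 8.2.2 (LDH) have no such rule.

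**What the protocol asks of participants who stop the drug.** Section 7.1: "If the study drug is definitively discontinued, the participant should remain in the study to be evaluated for safety follow up". Section 7.2 adds that "the participant should be encouraged to return for the remainder of his or her scheduled protocol visits until starting a different complement-targeted therapy". Section 2.3.1 gives a length: "Participants who discontinue the drug will be followed up for 16 weeks if participants remain in the study".

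**Disposition.** SAP 7.1 keeps the two events apart, listing among its categories "discontinued treatment, reasons for discontinuation of treatment, completing the study, switching to q6w dosing, discontinued from the study". No efficacy section uses that distinction.

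**Scoring of everyone else.** The FAS holds every participant with at least one dose (SAP 5.3), efficacy data are used as observed without imputation (SAP 6.3.1), and the endpoints in 8.1, 8.2.3 and 8.2.4 run to Day 351 with no on-treatment limit.

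**The concern.** The SAP evidently means a lack-of-efficacy exit to count against the regimen, but it ties that consequence to leaving the study. The protocol steers participants who stop the drug the other way, towards staying. The better a site follows Protocol 7.1 and 7.2, the less often the failure rule applies.

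The proportions are meant to show whether patients on high-dose eculizumab can be switched to the approved ravulizumab regimen. If stopping for lack of efficacy is a failure when the participant leaves, it should also be one when the participant stays. Otherwise the secondary proportions depend partly on who agreed to further visits.

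A related gap is that hemolysis or transfusion after ravulizumab has been stopped is not separated from events on the drug. Protocol 2.3.1 names serious hemolysis after discontinuation as a potential risk, although a theoretical one not seen in ravulizumab trials.

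**Working it through.** **1. The same stop, scored two ways.** Take two participants who stop ravulizumab on the same day for lack of efficacy, neither with a transfusion nor a hemoglobin fall of 2 g/dL or more. One leaves; one stays, as the protocol asks.

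| SAP section | Leaves the study | Stays in the study |
|---|---|---|
| 8.2.3 transfusion | Counted as transfused, no condition | Observed data: not transfused |
| 8.2.4 stabilized hemoglobin | Counted as not stabilized, no condition | Observed data: stabilized |
| 8.1 free C5-associated BTH | Counted if BTH with free C5 ≥ 0.5 µg/mL was recorded, or if free C5 ≥ 0.5 µg/mL at ET | Counted only if BTH with free C5 ≥ 0.5 µg/mL was recorded |
| 8.2.1 all BTH | Observed data | Observed data |

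The rows for 8.2.3 and 8.2.4 give opposite results. The 8.1 row differs only for a participant with free C5 at or above 0.5 µg/mL and no recorded free C5-associated BTH. The 8.2.1 row has no rule to misapply.

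**2. Stops for other reasons.** The leaver's data end at withdrawal. The stayer's events count to Day 351, on or off drug. The SAP does not say that this difference is intended.

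**3. The plan's own figures.** SAP 3.3: "The proposed sample size for this estimation study is approximately 20 participants". The intervals are Clopper-Pearson, with lower limit the 0.025 quantile of Beta(x, n − x + 1) and upper limit the 0.975 quantile of Beta(x + 1, n − x). With n = 20, all seven rows of the SAP 3.3 table reproduce after rounding:

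| Events | Plan | Recomputed |
|---|---|---|
| 19/20 | 75–100% | 75.1–99.9% |
| 15/20 | 51–91% | 50.9–91.3% |
| 10/20 | 27–73% | 27.2–72.8% |
| 5/20 | 9–49% | 8.7–49.1% |
| 2/20 | 1–32% | 1.2–31.7% |
| 1/20 | 0–25% | 0.1–24.9% |
| 0/20 | 0–17% | 0–16.8% |

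**4. Effect of rescoring.** Each rescored participant moves an estimate by 1/20 = 5 points. The documents give no discontinuation rate, and Protocol 7.1 expects permanent stops to be rare, so 0 to 2 is an assumed range.

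- None rescored: no change.
- One: 0/20 (upper limit 16.8%) becomes 1/20 = 5% (upper limit 24.9%), a rise of 8.1 points in the limit.
- Two: 2/20 = 10% (upper limit 31.7%), a further 6.8 points.
- Stabilized hemoglobin, for illustration: 18/20 = 90% (68.3–98.8%) becomes 17/20 = 85% (62.1–96.8%). These are the complements of 2/20 and 3/20 (3.2–37.9%).

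**5. How much off-drug time could be included.** Suppose the last infusion is on Day 127. Day 351 is 351 − 127 = 224 days later. Treating one q8w interval of 56 days as covered leaves 224 − 56 = 168 days. If follow-up ends 16 weeks (112 days) after the last dose, 112 − 56 = 56 days remain. A full 224 uncovered days would need a last infusion on Day 71 and attendance to Day 351. Starting another complement-targeted therapy shortens any of these.

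**The case against.** Four points carry weight.

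- **Everyone is already scored.** A reader might infer that the SAP assesses only participants who withdraw, or that drug failure goes uncounted in those who stay. The documents do not support that. Every FAS participant is scored on observed events, and a recorded free C5-associated BTH counts whether or not the drug is stopped. Uncontrolled hemolysis with a qualifying symptom or sign and LDH at or above 2 × ULN is BTH by definition. Even a lack-of-efficacy withdrawal enters the primary numerator only through the free C5 condition. This stands, and confines the effect on 8.1 to a narrow group.
- **Counting off-drug events is legitimate.** All treated participants and all events through Day 351 is a treatment-policy choice, and a conservative one for a switch study. It would be too strong to call it an error. What remains is that the choice is not stated, and that cutting off leavers' data at withdrawal while failing those who leave for lack of efficacy is not a consistent version of it. The documents also do not say whether sites record off-drug hemolysis on the BTH form.
- **No transfusion is a true observation.** So it is, but the SAP has already decided that a lack-of-efficacy exit overrides it. The objection is to applying that decision to leavers only.
- **The data can be inspected.** Exposure and efficacy data are listed by participant, reasons for stopping treatment are summarized, and no hypothesis is tested on these proportions. That limits the harm, but the reported proportion still follows the rule as written.

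The absence of lack of efficacy from the stopping reasons in Protocol 7.1 and 7.2 adds little, since both lists have a catch-all.

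**Conclusion.** The point holds in a limited form. The lack-of-efficacy rules have the wrong trigger: they respond to leaving the study when the event of interest is stopping ravulizumab. The consequence is clearest in SAP 8.2.3 and 8.2.4, where a participant who stops and stays can be a success while an identical leaver fails without condition. In SAP 8.1 it reaches only participants who stop for lack of efficacy with free C5 at or above 0.5 µg/mL and no recorded free C5-associated BTH. The mixing of on- and off-drug events is an unstated choice that calls for labelling and a sensitivity analysis, not for a different main analysis.

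The size is 5 points per rescored participant, assuming 20 in the FAS. How many there will be is unknown; if nobody stops for lack of efficacy and stays, the rescoring changes nothing.

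**What to change.** 1. In SAP 8.2.3 and 8.2.4, and for consistency in 8.1, change the trigger to: discontinue ravulizumab or withdraw from the study due to lack of efficacy.
2. In 8.1, for those who stay, use the free C5 sample at or closest to the decision to stop ravulizumab, not a late Day 351/ET sample that may reflect time off drug. Protocol Table 2 schedules no PK/PD sample at Day 239 or Day 295, so the SAP should say what applies if no nearby sample exists.
3. State that all events through Day 351 stay in the main analysis. Flag each as on- or off-treatment, using an analysis window after the last infusion that is fixed in advance.
4. Add one sensitivity analysis that excludes off-treatment events.

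Cost: SAP wording, one derived flag and one extra table. Infusion dates and reasons for stopping treatment are already planned for collection or summary; the reason list should be checked for a lack-of-efficacy category. The downside is a possibly less favourable secondary proportion.
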